**Table 1: Schedule of Treatments and Assessments**

Required Assessments	Screening			Procedure		Post-procedure follow up								
	SV1	2Wk	SV2	Procedure	DC	2Wk	1M	6Wk	8Wk	10Wk	3M	4M	6M	12M
Mode (O- in office, P-phone)	O	O	O			O	O	P 	P 	P 	O	O	O	O
Window (M-month, Wk-week, d-days)	--	±3 d			--	±3 d	±7 d	±3 d	±7 d	±3 d	±14 d	±7 d	±14 d	±30 d
Medical history	X													
Clinical assessment		X	X			X	X				X	X 	X 	X 
Renal denervation procedure				X										
OBP per study guidelines	X	X	X		X	X	X	X 	X 	X 	X	X	X	X
24h ABPM per study guidelines			X								X		X	X
Witnessed pill intake 													X	X
Medications prescribed 												X 		
Blood tests (Chem7) 			X		X		X				X		X	X
Serum or urine pregnancy test			X											
Drug testing			X								X			
Renal artery imaging- angiogram				X										
Renal artery imaging-DUS 													X	
Mortality assessment 						X	X	X	X	X	X	X	X	X
Medication and event review	X	X	X	X	X	X	X	X	X	X	X	X	X	X 

1: 4M follow-up is only required if 3M systolic OBP≥140 mmHg, prescribe AH medications according to **section 9.1.9** if SBP ≥ 140 mmHg

2: If medically necessary, phone contact may be replaced with office visit. OBP (per **Appendix 16.5**) to be obtained for an office visit or following alternative methods of data collection as described in **section 9.1.6**.

3: Witnessed pill intake (if subject is taking AH medications), complete after OBP measurements

4: Bicarbonate will not be measured for subjects enrolled in Europe.

5: DUS required as first line imaging modality at 6M. Repeat DUS, MRA, CT or angiogram to be used if DUS is nondiagnostic. Renal angiography must be used if repeat DUS/CTA/MRA is nondiagnostic or stenosis >60-70% is suspected. If renal imaging is not captured at the 6M follow-up visit due to extenuating circumstances, renal imaging is required at the next scheduled study visit.

6: Mortality assessment will be completed by the investigational site when a subject cannot be reached after each of the protocol required follow-up visits

7: SAE only review required at 12M visit

8: Clinical assessment of weight only

**Table 2: Schedule of testing through 12 months for subjects with office SBP  $\geq 180$  mmHg (confirmed via 2 sets of measurements) or escape via investigator discretion during off-medication period post-procedure**

Required Assessments	Procedure		Post-Procedure						
	Procedure	DC	2Wk	1M	6Wk	10Wk	3M	6M	12M
Mode (O- in office, P-phone)			O	O	O	O	O	O	O
Window (M-month, Wk-week, d-days)	--	--	$\pm 3$ d	$\pm 7$ d	$\pm 3$ d	$\pm 3$ d	$\pm 14$ d	$\pm 14$ d	$\pm 30$ d
OBP per study guidelines		X	X	X	X	X	X	X	X
Renal artery imaging 								X 	
Mortality assessment 			X	X	X	X	X	X	X
Medication and event review		X	X	X	X	X	X	X	X 

1: DUS required as first line imaging modality at 6M. Repeat DUS, MRA, CT or angiogram to be used if DUS is nondiagnostic. Renal angiography must be used if repeat DUS/CTA/MRA is nondiagnostic or stenosis  $>60$ -70% is suspected. If renal imaging is not captured at the 6M follow-up visit due to extenuating circumstances, renal imaging is required at the next scheduled study visit.

2: Mortality assessment will be completed by the investigational site when a subject cannot be reached after each of the protocol required follow-up visits

3: SAE only review required at 12M visit

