## 2. Synopsis

Title	Global Clinical Study of Renal Denervation in the distal main and first order branch renal arteries using the Symplicity Spyral™ multi-electrode renal denervation system (SPYRAL DYSTAL)
Clinical Study Type	Multi-center, international, prospective, interventional, single arm study
Product Name	The Symplicity Spyral™ multi-electrode renal denervation catheter (Symplicity Spyral™ catheter) and the Symplicity G3™ renal denervation RF generator (Symplicity G3™ generator)
EUDAMED number	CIV-19-12-031165
Sponsor	
Global sponsor: Medtronic Vascular, Inc. [name] United States
 
Regional sponsor: Medtronic Bakken Research Center (BRC) B.V. [name], The Netherlands
 
Note: this clinical study is funded by the Global sponsor.

Objective	The objective of this single arm interventional study is to determine if renal denervation performed in the distal main and first order branch renal arteries is as effective in reducing blood pressure as the procedural approach used in the SPYRAL HTN-OFF MED clinical study.
Product Status	Investigational in the United States. Commercially approved in countries that accept CE-mark. (Device will be used in accordance with the Instructions for Use .)
Endpoints	
Efficacy endpoints
 
The efficacy endpoints will be compared to the SPYRAL HTN-OFF MED efficacy endpoints using a propensity score stratified analysis at 3 months. At 6 months and 12 months, the endpoints will be analyzed within the SPYRAL DYSTAL study only.
 

• Change in systolic blood pressure (SBP) from baseline (Screening Visit 2) to 3, 6 and 12 months post-procedure as measured by 24-hour ambulatory blood pressure monitoring (ABPM).

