#### ***9.1.6. Follow -up Visits***

See **Table 3** for details on follow-up visit window and modality requirements for follow-up visits. See **Table 4** and **section 9.1.9** for escape subject requirements. Subjects will return for follow-up visits at 2 weeks, 1 month, 6 weeks, 8 weeks (non-escape only), 10 weeks, 3 months, 6 months, and 12 months post-procedure. Additionally, a 1 month and 4 month post-procedure in-office follow up is required for subjects with a systolic OBP >140 at the 3-month follow-up visit (see **section 9.1.10**).

Follow-up procedures for subjects treated are listed below and must be performed through 12 months follow up for each subject unless otherwise specified. After completion of the study required follow ups, the subjects will return to receiving standard of care follow up.

- **Clinical assessment** will be conducted at the 2 week, 1 and 3-months post-procedure follow-up visit to evaluate the subject's current medical condition. At 4, 6, and 12-months follow up an abbreviated clinical assessment of weight only is required.
- **Office blood pressure** measurements will be obtained in accordance with guidelines in **Appendix 16.5** at all follow-up visits.

- **Laboratory tests** are required at 1, 3, 6, and 12-month follow-up visits:
  - **Basic metabolic panel Chem-7 (blood)**: serum-creatinine, sodium, potassium, blood urea nitrogen (BUN) or urea, bicarbonate, chloride, and glucose. Bicarbonate will not be measured for subjects enrolled in Europe.
  - **eGFR** will be calculated from the serum-creatinine in the Chem-7 panel for eligibility criteria by using the 4 variable Modification of Diet in Renal Disease (MDRD) Formula.
- **Medication and adverse event reviews** will be completed at each follow-up visit to assess any changes in medication usage or medical condition:
  - Enrollment (consent) to 6-months follow up: all medications and all adverse events
  - After 6-months follow up to 12-months follow up: all medications and all serious adverse events

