- **Renal artery imaging** will be performed at the 6-month follow-up visit to assess if a renal artery stenosis is suspected. A renal duplex ultrasound (DUS) will be obtained at 6-months follow up and submitted to the DUS Core Laboratory. If the DUS is determined to be nondiagnostic a repeat DUS, a MRA, CT or angiogram will be performed (repeat imaging is to be completed within 30 days after confirmation of non-diagnostic imaging). If evidence of a clinically significant stenosis is indicated by the DUS or MRA/CT Core Laboratory, an angiogram must be obtained and submitted to the angiographic core laboratory.
  - If renal imaging is not obtained at the 6-month follow-up visit due to extenuating circumstances, renal imaging is required at the next scheduled study visit.
- **24-hour ABPM** will be conducted at the 3, 6, and 12-month follow-up visits post-procedure according to the guidelines in **Appendix 16.5**. A repeat ABPM will be required in the event of technical issues, failure to follow ABPM guidelines or if the minimum required number of daytime and nighttime readings is not obtained. If ABPM is repeated office blood pressure and drug testing (for 3-month follow up only) must be repeated on day the ABPM is applied.
  - Initiate medication re-Introduction for subjects with systolic OBP  $\geq 140$  mmHg at 3-month follow-up visit. Starting at the 3-month follow up after clinical assessment and a valid ABPM are completed.
- **Mortality assessment** will be completed by the investigational site when a subject cannot be reached after each of the protocol required follow-up visits.
- **Drug testing** (urine/blood) to ensure medications are no longer present in the subject's system. A urine sample will be collected, preferably using the subject's first morning urine. A blood sample will be collected at the time of the visit. Drug testing samples collected for subjects that screen fail after obtaining the sample, must not be sent to the core lab for analysis.

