### ***9.1.9. Anti-hypertensive medication escape criteria***

In the event a subject's office SBP  $\geq$ 180 mmHg, or there is a safety concern, from discharge up to and including the 3-month visit, the subject will be seen a second time within 72 hours for a repeat office BP. If the subject's office SBP remains  $\geq$ 180 mmHg, the subject will be put back on an antihypertensive medication regimen per the investigator's discretion. All efforts should be made to obtain an ABPM and Chem-7 panel, and urine and blood for antihypertensive drug testing, prior to the subject being put back on medications. If the subject already started medications, the subject and investigator should consider if it is safe to take the subject off medications for at least two weeks prior to the 3M visit in order to obtain the requirements at the 3-month visit to ensure endpoint data is collected. The subject will be exited from the off medications portion of the study and will be followed according to **Table 4**. If the subject's office SBP < 180 mmHg, the subject will continue to be followed per **Table 3**. At any time while the subject is not taking antihypertensive medications, either the subject or the investigator may restart antihypertensive medications if there is a safety concern and the subject will be followed according to **Table 4**. All blood pressures must be taken according to the guidelines in **Appendix 16.5** with the exception of needing to be completed by 10:30 am. Visits for monitoring the subject's BP for these purposes must be documented on the CRF.

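### Escape subjects have no scheduled 24-hour ABPM or Chem-7 at 6 and 12 months, so the late ambulatory results leave out a group defined by a post-procedure event; the gap is cheap to close

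*Protocol*

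**What the plan says.** The Synopsis lists change in 24-hour SBP from baseline "to 3, 6 and 12 months post-procedure as measured by 24-hour ambulatory blood pressure monitoring (ABPM") as an efficacy endpoint. It treats 24-hour DBP, office SBP and office DBP in the same way, and protocol 4.2.1 and SAP 7.7.2 repeat the list. At 6 and 12 months these endpoints are analysed within DYSTAL only.

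Protocol 9.1.6 says that ABPM "will be conducted at the 3, 6, and 12-month follow-up visits post-procedure" and that laboratory tests "are required at 1, 3, 6, and 12-month follow-up visits". It introduces its list of procedures as ones that "must be performed through 12 months follow up for each subject unless otherwise specified".

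Escape subjects are routed elsewhere. Section 9.1.6 says: "See Table 4 and section 9.1.9 for escape subject requirements". Section 9.1.9 says: "The subject will be exited from the off medications portion of the study and will be followed according to Table 4". Table 4, identical to Table 2, covers subjects with office SBP of at least 180 mmHg ("confirmed via 2 sets of measurements) or escape via investigator discretion during off-medication period post-procedure"). Section 9.1.9 also lets the subject or the investigator restart drugs for a safety concern. Tables 2 and 4 have a row for "OBP per study guidelines" at every post-procedure visit, but none for ABPM, witnessed pill intake or blood tests.

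**The concern.** An escape subject attends the office at 6 and 12 months and has office pressure taken, but under the schedule cannot supply the ambulatory value that is an endpoint at the same visit. The ambulatory mean then describes subjects who did not escape, a set fixed by something that happened after the procedure. If the office mean includes escape subjects, the two late results describe different groups and cannot be read side by side. A wider confidence interval would not reveal this.

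Being on drugs does not explain the omission. Under protocol 9.1.10, subjects with office SBP of at least 140 mmHg at 3 months also restart drugs, and Tables 1 and 3 keep their ABPM and Chem-7 at 6 and 12 months. Comparability with HTN-OFF MED does not explain it either, because the late endpoints have no comparator.

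There is a smaller safety counterpart. With no scheduled creatinine, an escape subject could be counted as free of a creatinine rise without having been tested.

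**Working it through.** **1. Schedules at 6 and 12 months, side by side**

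| Assessment | Tables 1 and 3 | Tables 2 and 4 (escape) |
|---|---|---|
| Office BP | 6M, 12M | 6M, 12M |
| 24-hour ABPM | 6M, 12M | no row |
| Witnessed pill intake | 6M, 12M | no row |
| Chem-7 | 6M, 12M | no row |
| Renal imaging | 6M | 6M |
| Medication and event review | 6M, 12M | 6M, 12M |

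**2. Does any rule restore the ambulatory values?**
- Carry-forward for escape subjects (SAP 7.1.3.1) uses readings up to 3 months only.
- SAP 7.3 rules out other imputation.
- SAP Appendix III admits only scheduled follow-up ABPMs, so one done at an unscheduled visit would not enter.

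None does. At 3 months there is partial cover, from carry-forward and from the request in protocol 9.1.9 for an ABPM before drugs restart. At 6 and 12 months there is none.

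**3. The plan's own figure.** Protocol 13.3 gives, for 38 subjects, a 24-hour SBP change of -5.5 mmHg, 95% CI -9.1 to -2.0, p = 0.003.
- Half-width = (9.1 - 2.0)/2 = 3.55.
- SE = 3.55 / t(0.975; 37 df) = 1.752.
- SD = 1.752 x sqrt(38) = 10.8.
- t = -5.5/1.752 = -3.14, two-sided p = 0.0033, which agrees with the stated 0.003.

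**4. Size.** Let k be the number of escape subjects among 50 treated and D the mean BP change in escape subjects minus that in the others. The all-treated mean minus the non-escape mean is (k/50) x D. The documents give neither k nor D, so both are assumed, with 10 mmHg for the absolute value of D. The 95% half-width is t(0.975; n-1) x 10.8/sqrt(n), where n = 50 - k. At n = 50 it is 3.07 mmHg.

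| Assumed escape rate | k | Ambulatory n | Half-width (mmHg) | Shift for 10 mmHg (mmHg) |
|---|---|---|---|---|
| 4% | 2 | 48 | 3.14 | 0.4 |
| 10% | 5 | 45 | 3.24 | 1.0 |
| 20% | 10 | 40 | 3.45 | 2.0 |

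The shift is zero if D is zero and scales in proportion to D. The table assumes no other missing data. The SD of 10.8 is a 3-month, off-drug figure from HTN-OFF MED, so it only indicates scale at 6 and 12 months.

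**5. Creatinine.** SAP 7.7.1 puts in the denominator anyone with an adjudicated event or with last contact beyond the lower window (day 166 for 6 months). An escape subject who attends the 6-month visit on day 180 qualifies by contact date, but has no scheduled creatinine that could reveal an event. With one event and k = 5, the rate would be 1/50 = 2.0% on that denominator and 1/45 = 2.2% among subjects with a scheduled draw. The SAP words the algorithm for adjudicated events and exempts creatinine from adjudication, so whether it applies to creatinine is itself unclear.

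**The case against.** The strongest reply is that this is a deliberate choice with little riding on it. Much of that stands.

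- *A reader might infer that section 9.1.6 and Table 4 contradict each other.* They do not. The list in 9.1.6 is qualified, and Table 4 is the exception it allows. This is a gap between the schedule and the endpoints.
- *A reader might infer that the office endpoints keep escape subjects.* The documents do not say so. ITT, modified ITT and per-protocol BP outcomes are all described only to 3 months. A set that excluded escape subjects would remove them from both endpoints. SAP Appendix II also writes its office BP selection rules for visits with one or more ABPM records and is silent on visits with none.
- *A reader might infer that treatment failures are being dropped and the late result flattered.* Escape also covers safety concerns and restarts by subject or investigator. By 6 months many other subjects may be back on drugs too, so the sign is open.
- *Existing safeguards.* Protocol 13.7 has the number in each analysis reported, SAP 7.6 summarises drug use at each follow-up, and protocol 9.1.9 seeks a Chem-7 before restart. Section 9.1.7 provides for unscheduled creatinine draws. These make the differing denominators visible, but they do not supply the missing values.
- *Cost.* New rows require an amendment with the approvals in protocol 14.6, and section 5 lists blood tests, and ABPM except in several EU countries, as outside standard of care. This is fair, and argues for bundling the change with another.

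**Conclusion.** The point holds as a cheap improvement. Followed exactly, the plan yields 6- and 12-month ambulatory results without escape subjects, while office pressure is taken from them at the same visits and may or may not be analysed. No stated rule fills the gap, and no stated reason explains it.

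The likely effect is modest. Under the assumptions shown it is 0.4 to 2.0 mmHg in either direction, inside the half-width of about 3.1 mmHg for 50 subjects. The escape rate, the 10 mmHg difference and complete attendance are assumptions. The creatinine consequence depends on how SAP 7.7.1 is applied.

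The endpoints concerned are descriptive, without a comparator or formal hypothesis. Nothing here touches the 3-month comparison with HTN-OFF MED.

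**What to change.** 1. **Protocol Tables 2 and 4.** Align the 6- and 12-month outcome-measurement rows with the endpoints and with Table 1: 24-hour ABPM together with its witnessed-pill-intake row, and Chem-7. This is data collection only and changes no treatment rule.
2. **SAP 7.7.2.** Name the analysis set for the 6- and 12-month endpoints. Where escape subjects lack ABPM, label the ambulatory results 'non-escape subjects only' and repeat the office BP results in that same subset.
3. **SAP 7.7.1.** Count only subjects with a creatinine value in the denominator of the creatinine endpoint.

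Item 1 costs a few extra ABPMs and blood draws at visits these subjects already attend, with monitors the sites already hold, plus a protocol amendment that can travel with the next one. Items 2 and 3 are a few sentences in the SAP and remain useful even if item 1 comes too late for some subjects.

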### 3. Introduction

#### 3.1. Background

Chronic activation of the sympathetic nervous system (SNS) has been identified by preclinical and clinical literature as a common and key factor in disease states such as hypertension, heart failure, and chronic kidney disease. The renal sympathetic nerves are a major contributor to the complex pathophysiology of elevated SNS activity and hypertension. Therapeutic renal denervation, the deliberate disruption of the sympathetic nerves connecting the kidneys with the central nervous system, has been shown to be an effective means of modulating elevated SNS activity - both by reducing the sympathetic control of renal function (renin release, sodium excretion and renal blood flow) and by removing the renal afferent sympathetic contribution to central sympathetic elevation. It is important to note that the kidneys maintain appropriate electrolyte and volume homeostasis, despite being denervated, as demonstrated by the human kidney transplant experience. Prior to pharmacological treatment, hypertension was sometimes treated with complex invasive procedures, such as surgical nephrectomy and even radical surgical sympathectomy.

Medtronic has developed a radiofrequency catheter with multiple electrodes, as a minimally invasive means of achieving renal sympathetic denervation. Bilateral renal denervation will be performed using a percutaneous, catheter-based system that delivers radiofrequency (RF) energy through the luminal surface of each renal artery at four locations simultaneously. In comparison to the previous single-electrode Symplicity™ renal denervation system, the multi-electrode catheter provides the physician with a pre-defined and consistent ablation pattern that is intended to improve the accuracy of treatment. The RF energy may be delivered to up to 4 electrodes simultaneously. If the physician elects to complete multiple treatments in one artery, subsequent treatments are easily accommodated by re-positioning the catheter proximally (at least 5 mm) and de-selecting electrodes via the graphical user interface on the Symplicity G3 generator. The electrodes are mounted on to a self-expanding Nitinol shaft that takes a spiral configuration allowing electrode contact with the vessel wall. An evaluation of the results of pre-clinical (*in-vivo*) and *in-vitro* testing supporting the use of the Symplicity Spyral catheter and Symplicity G3 generator as investigational devices in human subjects is included in the Investigator's Brochure. Medtronic has performed a comprehensive set of bench testing and preclinical studies that have shown that this manner of low-power ablation produces distinct, focal, sterile lesions that subsequently heal, resulting in no clinically relevant long-term sequelae to either the vessel or the kidney.

The currently ongoing SPYRAL PIVOTAL – SPYRAL HTN-OFF MED and SPYRAL HTN-ON MED studies are multi-center, international, single blind, randomized, sham-controlled studies designed to evaluate the effect of renal denervation on blood pressure. The SPYRAL PIVOTAL – SPYRAL HTN-OFF MED study is evaluating the effect of renal denervation in the absence of antihypertensive medications, whereas the SPYRAL HTN-ON MED study is evaluating the effect of renal denervation on standard medical therapy.

Preliminary data on the first 80 randomized subjects with three months follow up within the SPYRAL HTN-OFF MED study were published in August 2017 in *The Lancet*. The mean difference between the groups favored renal denervation for 3-month change in both office and 24-h blood pressure from baseline: 24-h SBP  $-5.0$  mm Hg (95% CI  $-9.9$  to  $-0.2$ ;  $p=0.0414$ ), 24-h DBP  $-4.4$  mm Hg ( $-7.2$  to  $-1.6$ ;  $p=0.0024$ ), office SBP  $-7.7$  mm Hg ( $-14.0$  to  $-1.5$ ;  $p=0.0155$ ), and office DBP  $-4.9$  mm Hg ( $-8.5$  to  $-1.4$ ;  $p=0.0077$ ). Baseline-adjusted analyses showed similar findings. There were no major adverse events in either group. Additionally, preliminary data on the first 80 randomized SPYRAL HTN-ON MED subjects with six months follow-up were published in May 2018 in *The Lancet*. Office and 24-h ambulatory blood pressure decreased significantly from baseline to six months in the renal denervation group: 24-h SBP  $-7.0$  mm Hg, 95% CI  $-12.0$  to  $-2.1$ ;  $p=0.0059$ , 24-h DBP  $-4.3$  mm Hg,  $-7.8$  to  $-0.8$ ;  $p=0.0174$ , office SBP  $-6.6$  mm Hg,  $-12.4$  to  $-0.9$ ;  $p=0.0250$ , and office DBP  $-4.2$  mm Hg,  $-7.7$  to  $-0.7$ ;  $p=0.0190$ ). The change in blood pressure was significantly greater at six months in the renal denervation group than the sham-control group for office SBP (difference  $-6.8$  mm Hg, 95% CI  $-12.5$  to  $-1.1$ ;  $p=0.0205$ ), 24-h SBP (difference  $-7.4$  mm Hg,  $-12.5$  to  $-2.3$ ;  $p=0.0051$ ), office DBP (difference  $-3.5$  mm Hg,  $-7.0$  to  $-0.0$ ;  $p=0.0478$ ), and 24-h DBP (difference  $-4.1$  mm Hg,  $-7.8$  to  $-0.4$ ;  $p=0.0292$ ).

These initial results from both studies provided biological proof of principle for the blood-pressure-lowering efficacy of renal denervation. The safety profile within these published cohorts showed no major adverse events.

In order to test the hypothesis in the SPYRAL PIVOTAL - SPYRAL HTN-OFF MED study that renal denervation decreases blood pressure and is safe when studied in the absence of antihypertensive medications, study subjects were randomized to the Denervation or Control group in a 1:1 fashion. In addition to subjects being blinded to their randomization assignment, site personnel involved in the measurement of office blood pressure were also blinded to study subjects' randomization assignment through the primary endpoint to prevent potential bias of results. Subjects were studied in the absence of antihypertensive medications to assess the impact of renal denervation on systolic blood pressure in the absence of medication.

Study enrollment was stopped for efficacy after the first interim analysis in February 2020. Data from the initial 80 patients with three months follow up from the SPYRAL HTN-OFF MED study was combined with data from the initial 251 patients with three months follow up from the SPYRAL PIVOTAL-SPYRAL HTN-OFF MED study and was presented at ACC World Congress of Cardiology in March 2020. Concurrently, an article presenting the data was published in *The Lancet*. A brief summary of the SPYRAL PIVOTAL-SPYRAL HTN-OFF MED data is provided below.

The primary endpoint, change in 24-h blood pressure at three months, was compared between groups. Drug surveillance was done to ensure patient compliance with absence of antihypertensive medication. The primary analysis was done in the intention-to-treat population. Safety events were assessed to three months.

From June 25, 2015, to Oct 15, 2019, 1519 patients were enrolled, of whom 1188 were excluded because they did not meet inclusion criteria. 166 were randomly assigned to renal denervation and 165 to the sham procedure (80 were included in the pilot and 251 in Pivotal).

There were no major safety events reported at one month. There was one major safety event in each treatment group up to three months (one admission to hospital for hypertensive crisis or emergency in the renal denervation group and one new stroke in the sham procedure group), and neither was attributed to the device or trial procedures.

For the primary efficacy endpoint of changes from baseline in 24-h systolic blood pressure at three months, there was a significant difference between the renal denervation and sham procedure groups. This endpoint was met with a posterior probability of superiority greater than 0.999 and a treatment difference of -3.9 mm Hg (95% BCI -6.2 to -1.6). For the secondary efficacy endpoint of difference in three-month changes in office systolic blood pressure between the two groups, the difference was significant, and the endpoint was met (difference -6.5 mm Hg (95% BCI -9.6 to -3.5), with posterior probability of superiority of more than 0.999. The blood pressure changes analyzed using the prespecified ANCOVA-adjusted frequentist analysis of the overall population show similar changes in blood pressure to Bayesian results.

Besides the “confounding factors” analysis of SYMPLICITY HTN-3 indicating that the blood pressure response to renal denervation may depend on the number of lesions applied, few studies have shown a strong relationship between the number of lesions delivered and subsequent blood pressure reduction. These new results indicate that the location of the lesion, i.e., the distal main and branches, may be an important factor in blood pressure reduction.

Both SPYRAL HTN-OFF MED and SPYRAL HTN-ON MED trials used the same RDN technique, applying treatments in eligible renal arteries and the branches, and presented similar results in three and six months follow-up, respectively. In the SPYRAL HTN-OFF MED trial, on average  $17.9 \pm 10.5$  ablations were performed in the main renal arteries, and an additional  $25.9 \pm 12.8$  ablations were performed in branch vessels.

Recently Petrov and colleagues evaluated renal denervation therapy beyond the proximal main renal artery (Y-pattern), including the primary branches, and compared it to the standard procedure applied only within the main vessel. In 80 patients treated with the standard ablation using the first generation Symplicity “Flex” catheter,  $12.0 \pm 3.0$  total ablations (both sides) were applied while  $20.4 \pm 3.9$  total ablations were delivered for the group of 39 patients with Y-pattern denervation ( $P < 0.001$ ). Renal denervation was associated with significant decreases in both office and ambulatory systolic and diastolic blood pressure in both groups. The reduction in 24-hour mean ambulatory systolic blood pressure at six months was significantly greater ( $P = 0.002$ ) for the Y-Pattern group ( $-22.1 \pm 15.4$  mm Hg) compared to the Standard group ( $-11.8 \pm 16.2$  mm Hg). Changes in diastolic office and ambulatory pressure were also

significantly greater at six months in the Y-pattern ablation group. These findings support the benefit of improved blood pressure reduction by including denervation of nerves in the renal artery branch vessels.

Similarly, Pekarskiy and colleagues compared renal denervation therapy in the distal main vessel and the arterial branches to ablation in the proximal main artery in 51 randomized hypertensive subjects. The magnitude of the 24-hour pressure drops at six months post-procedure for the “distal” approach was significantly higher than the “traditional” approach achieved using the Symplicity Flex denervation system ( $22.6 \pm 20.0$  vs  $9.4 \pm 18.7$  mm Hg;  $P < 0.05$ ).

In a dual-center prospective analysis, Fengler and colleagues reported comparative efficacy and safety between a group of 25 treatment resistant hypertension patients treated with ablation of main renal artery, side branches, and accessory arteries to a matched control group ( $N = 25$ ) with only main renal artery ablation. Systolic 24-hour mean ABP decreased significantly after three months in the combined ablation group ( $-8.5 \pm 9.8$ / $-7.0 \pm 10.7$  mm Hg,  $P < 0.001/0.003$ ), but not in patients with main artery treatment ( $-3.5 \pm 11.1$ / $-2.0 \pm 7.6$  mm Hg,  $P = 0.19/0.20$ ) and systolic daytime BP was significantly lower in patients with combined ablation compared to main artery ablation ( $P = 0.033$ ).

The results of the preclinical IVY study using norepinephrine drop and cortical axon area density as alternative indices to blood pressure drop when main vessel ablation was augmented with branch therapy treatment in a long-term study in pigs also shows a trend towards greater office blood pressure reduction.

A post hoc analysis of a previously reported single center non-randomized study from Kiuchi and colleagues analyzed the correlation between the number of lesions and blood pressure drop according to lesion location supporting the concept of targeting the distal part of the main renal artery and the branches rather than increasing the number of RF applications in the main renal artery. Thirty patients with “resistant” hypertension and CKD received renal denervation with a cardiac EP catheter. Mean 24-hour systolic blood pressure decreased by 21 mmHg at two years. An average of 17 total lesions (right plus left) were applied, including an average of 5 proximal, 5 mid, 5 distal, and 2 branch lesions. The total number of ablations was not correlated with BP drop. However, the number of lesions applied in the branches was linearly associated with 24-hour SBP-lowering effect at both 12 and 24 months of follow up. The strongest correlation between the number of lesions and blood pressure drop was observed when combining distal main plus branch lesions. The results suggest that focusing therapy on the distal main and branches may increase blood pressure reduction.

Besides one HTN-3 post hoc analysis, no trial (including SPYRAL HTN-ON and -OFF MED) has shown a correlation between the total number of lesions and BP reduction. The number of RF lesions did not correlate with BP reduction, unless the lesions were delivered to the branches.

As compared to the currently recommended procedure specified in the SPYRAL HTN ON and OFF MED trials, a procedure focused on the distal main renal arteries and first order branches suggests similar safety

and blood pressure reductions but with potential for shorter procedural times, less radiation exposure, and less contrast usage.

